As part of the screening process, clinical histories, physical examinations including vital signs, and photography of sun exposed and non sun-exposed arm will be performed. Cutometry, Raman spectroscopy (Biophotonic scanning) and transepidermal water loss will be measured.

Enrollment Visit (VISIT 2—subset of 30 participants from the older group above will be invited for this visit)

Upon enrollment into the study, patients will be instructed on proper usage topical retinol versus vehicle placebo. The placebo versus treatment arm will be clearly labeled on the subject's diary to minimize subject error. Participants will apply treatment to one arm and placebo to the other arm based on computer generated randomized assignment of left or right for the retinol. Participants are blinded to the treatment. Participants will be given a diary to record adherence to study procedures. Participants will be instructed to discontinue study if there is any itching or burning sensation that is moderate or severe and to contact study personnel immediately should this occur.

Week 12 visit (VISIT 3—the 30 participants from VISIT 2 (older group) only)

Adverse events and concomitant medication changes will be assessed and recorded. Study diary will be reviewed for adherence to study regimen. Photographs, cutometry and TEWL measurements will be taken. Two 4 mm skin biopsies will be taken at this time, one from the side with the retinol exposure and one from the side without retinol exposure after injection of a small amount of lidocaine anesthetic. Skin biopsies will be bisected and placed in either formalin for hematoxylin and eosin staining and mucin staining (for GAG), or placed into RNA later for subsequent gene expression analysis by 3'-end sequencing as described in Chang et al., 2013. Tissue will also be sent for microRNA analysis.

VISIT 1—age<25 years group only

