Whole transcriptome libraries will be created from the samples stored in RNA later and sent for 3'-end sequencing at Stanford Functional Genomics Core Facility after de-identification. We have utilized this Core facility for other projects in the past with high quality results. Results will be analyzed by our bioinformatician using the methods outlined in Chang ALS *et al.*, 2013. Specifically, comparisons will be made in skin from older participants between the pre and post treatment compared to placebo. All results of interest from 3'-end sequencing will be confirmed by RT-qPCR.

We anticipate that the adverse event rate (deemed related to study agent by investigator) for participants is less than 10% and may include mild (grade 1) itching or burning.

Significance

This study will be the first broad based, unbiased investigation into the molecular basis of the anti-aging effects of topical vitamin A. This study is a high quality, well-controlled study using state-of-the art technology of 3-Seq and microRNA analysis. Our research group has established the workflow from previous larger studies in skin aging (unpublished data) and can now leverage this experience for maximal efficiency and positive results. Specifically, we would be able to compare our results to inner arm skin from females younger than 30 years whose gene expression profiles are already contained in our database.

Confidential Stanford University School of Medicine

This study will provide novel candidate gene pathways as well as confirm suspected/known genes important for skin rejuvenation in humans. This information will aid in discovery of new topical agents that might have rejuvenative capacity due to their ability to mimic aspects of the vitamin A gene expression changes.

References

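### No masking is stated for the Week 12 cutometry and TEWL operators or for the investigator judging relatedness, and the diary label, read literally, shows which arm has retinol

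*Combined protocol and SAP*

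**What the plan says.** The design is within-person: each participant uses retinol on one arm and vehicle on the other, by "computer generated randomized assignment of left or right for the retinol" (Enrollment Visit, VISIT 2). The same section says "Participants are blinded to the treatment". It also says of the diary, which the participant is given: "The placebo versus treatment arm will be clearly labeled".

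The Week 12 visit (VISIT 3) section then lists, in this order:

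1. "Adverse events and concomitant medication changes will be assessed and recorded".
2. "Study diary will be reviewed for adherence to study regimen. Photographs, cutometry and TEWL measurements will be taken".
3. Two 4 mm biopsies, "one from the side with the retinol exposure and one from the side without retinol exposure".

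Anticipated Results states blinded assessment for two outcomes: photographs, by a dermatologist, and histology, by a dermatopathologist. The paragraph there on cutometry and TEWL says nothing about masking. Nor does the later statement on the "adverse event rate (deemed related to study agent by investigator", which is given for participants and not per arm.

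**The concern.** Both arms of a participant are measured side by side at one visit. An operator who knows which arm had retinol could influence the contrast directly, for example through where the probe is placed or whether a reading is repeated. For photographs and histology a blinded reader stands between the operator and the result. For cutometry and TEWL none is stated, so the operator's reading is the data.

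These readings are not incidental. Specific Aim 2 covers biometrics as well as wrinkling, and Anticipated Results predicts statistically significant differences between treated and placebo arms in cutometry and TEWL. It gives no direction, but the expectation of a difference is written into the plan. Specific Aim 3 concerns adverse events, and relatedness is an investigator judgement with no masking stated.

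The participant is affected too. If the diary names the placebo and treatment arms, its holder is not blinded, and reports of itching or burning could be coloured by that knowledge.

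**Working it through.** The plan states no figure on this point, so the main check is to set the statements side by side.

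**Who is stated to be masked**

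| Party | Masking stated? | Section |
|---|---|---|
| Participant | Yes, but in conflict with the diary label read literally | Enrollment Visit |
| Dermatologist grading photographs | Yes | Anticipated Results |
| Dermatopathologist | Yes | Anticipated Results |
| Photographer, biopsy operator | No | Week 12 visit |
| Cutometry and TEWL operators | No | Week 12 visit; Anticipated Results |
| Investigator judging relatedness | No | Anticipated Results |

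**How the allocation could reach Week 12 staff**

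- *Diary.* If the label is literal, whoever reviews the diary sees the allocation. The review is listed just before the measurements. The text neither assigns the two tasks to different people nor says that the label is coded.
- *Biopsy wording.* The sides are named by treatment instead of left and right. That invites staff to look up the allocation but does not require it.
- *Allocation list.* No holder is named.

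**How far the diary argument reaches.** Adverse events are listed before the diary, so the order of tasks says nothing about them. For relatedness, all that can be said is that masking is not stated.

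**Is masking feasible?** Yes. Materials and Methods reports no discernible difference between the two lotions in colour, odour or consistency.

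**Illustrative size**

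Inputs: n = 30 (the Enrollment and Week 12 headings); two-sided 0.05, taken from Statistical Considerations and applied here to a paired t-test. Assumption: operator knowledge adds a constant shift of d SDs of the paired differences, and there is no true effect. The documents give no value for d.

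The t statistic is then noncentral t with 29 degrees of freedom and noncentrality d√30. The critical value is 2.045. The rejection probability is P(|T| > 2.045).

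| Assumed d | d√30 | False-positive rate, n = 30 |
|---|---|---|
| 0.02 | 0.110 | 0.051 |
| 0.05 | 0.274 | 0.058 |
| 0.1 | 0.548 | 0.083 |
| 0.2 | 1.095 | 0.185 |
| 0.3 | 1.643 | 0.355 |

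With the plan's 10% dropout, 30 × 0.9 = 27 complete. The rates at 0.1, 0.2 and 0.3 SD become 0.079, 0.170 and 0.324.

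**The case against.** A reader might infer that Week 12 staff must know the allocation. The documents do not support that, for these reasons:

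- Every participant has one biopsy from each arm. The operator can sample left and right, label by side and link to treatment later. The biopsy sentence describes what is sampled, not what the operator knows.
- The Week 12 tasks appear in successive sentences. The order is not said to be binding, and nothing says that one person does them all.
- The diary label might be a code. If so, the route through the diary closes and the conflict with participant blinding disappears.

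All three stand as limits on the claim, but none supplies the missing statement. The text does not say that the label is coded, that the tasks are separated or that the operators are masked, although it states blinding explicitly elsewhere.

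A reader might also infer that relatedness is judged after the allocation has been seen, or that adverse events are attributed arm by arm. The listed order and the participant-level rate do not support either.

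A further objection is that biased photographs or biopsy sites are conjecture, since grading and histology reading are blinded. That is fair, and it narrows the main exposure to cutometry, TEWL and adverse event attribution. The false-positive figures are also open to objection: they rest wholly on an assumed shift, and at 0.02 SD the rate is barely above nominal.

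**Conclusion.** The concern holds as a gap with a written route to the allocation. Staff could know which arm had retinol when they take cutometry and TEWL readings, and nothing in the plan prevents it. That they do know it is not established. The diary label, read literally, also contradicts participant blinding, and the two statements need reconciling. For adverse events, only the absence of stated masking can be claimed.

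The documents do not fix a size. Under an assumed shift of 0.05 to 0.3 SD with n = 30, the false-positive rate is about 6% to 36%. This shows sensitivity and does not estimate bias in this trial. The blinded grading of fine wrinkling and the blinded histology reading are not called into question. The point deserves correction because Specific Aims 2 and 3 depend on the exposed outcomes and the remedy is cheap.

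**What to change.** - Label the diary and the lotion containers left arm and right arm, or by code, instead of placebo and treatment. This also removes the conflict with participant blinding.
- Identify every image, reading and biopsy by participant number and left or right.
- In the Week 12 section, name the biopsy sides as left inner arm and right inner arm, at mirrored sites fixed in advance.
- State that the cutometry and TEWL operators and the investigator judging relatedness are masked.
- Name who holds the left/right list, keep it away from Visit 3 staff, and merge it only after readings, gradings and relatedness calls are locked.

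Leave the adverse event and medication assessment where it is in the visit. Diary review may move after the measurements, but once the diary is coded this is not needed.

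The cost is mainly labelling and protocol text. No procedure is added, but someone other than the Visit 3 staff must hold the list; the documents do not say whether such a person is already in place. One small downside is that the allocation must be looked up if a reaction requires it.

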As part of the screening process, clinical histories, physical examinations including vital signs, and photography of face, sun exposed and non sun-exposed arm skin will be performed. Cutometry, Raman spectroscopy (non invasive Biophotonic scanning) and transepidermal water loss will be measured. Photographs, cutometry and TEWL measurements will be taken. A 4 mm skin biopsies will be taken from the inner arm skin after injection of a small amount of lidocaine anesthetic. Skin biopsies will be bisected and placed in either formalin for hematoxylin and eosin staining and mucin staining (for GAG), or placed into RNA later for subsequent gene expression analysis by 3'-end sequencing as described in Chang *et al.*, 2013. Tissue will also be sent for microRNA analysis.

Statistical Considerations

This study is powered using data from Kafi et al. for the primary clinical endpoint of fine

wrinkling score as measured by semi-quantitative scale of 0 to 9. A sample size of 36 provides a power level of 0.80 in detecting a difference of 1.00 unit on mean value before and after treatment for the fine wrinkling scale, with a type I error rate of 0.05 for a 2-tailed hypothesis, assuming a standard deviation of differences to be 1.8. Assuming a dropout rate of 10%, the sample size needed is 28 subjects.

Anticipated Results

Results of photographs will be analyzed in blinded fashion by a board certified dermatologist for skin aging parameters including fine wrinkling (tertiary endpoint), dyspigmentation, and surface texture with results graded on a 9 point Likert scale per Kafi *et al.* We anticipate that there will be statistically significant differences in mean score of these parameters between pre- and post- treatment groups for both vitamin A and placebo.

Results of histology will be evaluated in blinded fashion by a dermatopathologist. Parameters of skin aging will include measurement of epidermal thickness, and density of collagen and elastin. Results from the pre- and post- treatments groups for topical vitamin A versus placebo will be compared.

Results of the cutometry and TEWL measurements will be grouped and mean and standard deviations for the older patients before and after topical vitamin A treatment will be calculated and compared to placebo. We anticipate there will be statistically significant differences in the mean scores in cutometry and TEWL measurements between treated and placebo groups.

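### The power statement is wrong as written: on its own inputs 36 participants give 0.90 power, not 0.80, and the 10% dropout allowance lowers the number to 28 instead of raising it

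*Combined protocol and SAP*

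**What the plan says.** The Statistical Considerations section sizes the study on the fine wrinkling score, a 0 to 9 scale that it calls the primary clinical endpoint. It states: "A sample size of 36 provides a power level of 0.80 in detecting a difference of 1.00 unit". The difference is "on mean value before and after treatment for the fine wrinkling scale", the type I error rate is 0.05 two-tailed, and the variability is given by "assuming a standard deviation of differences to be 1.8". The next sentence concludes: "Assuming a dropout rate of 10%, the sample size needed is 28 subjects".

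A third number appears in the visit schedule. The Enrollment Visit (Visit 2) heading describes a "subset of 30 participants from the older group above will be invited for this visit", and the Week 12 visit (Visit 3) heading refers to "the 30 participants from VISIT 2 (older group) only". Neither heading links 30 to the 36, the 28 or the 10% dropout rate.

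**The concern.** Two things look wrong on reading. A standardised difference of 1.00/1.8 = 0.56 in a paired design should need fewer than 36 participants for 0.80 power. And the text moves from 36 down to 28 when it allows for dropout, which is the wrong direction whatever the test.

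This is the plan's only justification of its size. A reader cannot tell what the 28 counts. Taken at face value, the 36 also makes the planned 30 look short of its requirement, which the stated inputs do not support.

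**Working it through.** **Inputs, all from Statistical Considerations:** difference δ = 1.00; SD of differences σ = 1.8; two-sided α = 0.05; target power 0.80; dropout 10%. The planned 30 comes from the Visit 2 heading. No test is named; a paired t-test is inferred from the SD of differences.

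**Formula.** Power = P(|T| > t(0.975, n−1)), where T is noncentral t with n−1 degrees of freedom and noncentrality (δ/σ)√n.

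**The plan's figure, n = 36.** Noncentrality = (1.00/1.8) × 6 = 3.33; critical value 2.030; power = **0.900**. The stated 0.80 is not reproduced.

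**Other sample sizes, same inputs:**

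| n evaluable | Where it comes from | Paired-t power |
|---|---|---|
| 25 | 28 less 10% (25.2) | 0.760 |
| 26 | possible intended value of 36 | 0.777 |
| 27 | 30 less 10% | 0.794 |
| 28 | stated after dropout | 0.809 |
| 30 | planned, no dropout | 0.837 |
| 36 | stated for 0.80 | 0.900 |

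Solving for n gives 27.41 for 0.80 power, so 28, and 36.02 for 0.90 power. The 36 is therefore almost exactly the number for 0.90.

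**Can another method give 0.80 at 36?**

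- Normal approximation: Φ(6/1.8 − 1.960) = 0.915.
- One-sided paired t-test: 0.948, and it contradicts the stated two tails.
- Wilcoxon signed-rank at its lower efficiency bound of 0.864: 36 × 0.864 = 31.1 effective participants, power about 0.85.
- Two independent groups, taking 1.8 as the SD within each: 0.64 with 36 per group, 0.37 with 36 in total.
- Alpha split three ways (0.05/3): 0.789, close to 0.80, but it contradicts the stated 0.05.
- Keeping the paired t-test and α = 0.05, 36 gives 0.80 only if the SD is 2.08 or the difference is 0.86. Neither is stated.

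**Dropout step.** Correct inflation is n/(1 − 0.10): 36/0.9 = 40, and 28/0.9 = 31.1, so 32. The cruder 36 × 1.1 = 39.6 also goes up. Even the mistake of multiplying by 0.9 gives 32.4. No version turns 36 into 28.

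**Where 28 could come from.** There are two routes:

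- It is the paired-t number for 0.80 power before any dropout.
- It is the normal-approximation number plus 10%: (1.960 + 0.842)² × 1.8² = 25.43, and 25.43 × 1.1 = 27.97.

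On the first route 28 means evaluable participants; on the second it means enrolled.

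**The case against.** The strongest reply is that there is one slip, not two. If 36 should read 26, the normal approximation gives 25.43, rounded up to 26 with power 0.81. Adding 10% to 25.43 gives 28, so the dropout step then goes the right way. On that reading the 28 is sound, the planned 30 exceeds it, and no enrolment number changes. The same reading uses the normal approximation, under which 25 evaluable give 0.79, so the 0.76 from the t-test overstates what the planners themselves would have computed.

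This is plausible, but the documents do not establish it. The exact paired t-test gives 0.777 at 26, and 26/0.9 = 28.9 rounds to 29, not 28. The reading that 36 is the 0.90-power number and 28 the 0.80-power number fits about as well, although strict rounding of 36.02 gives 37. What stands is that this may be a single-digit error and that its practical effect is small. What does not stand is leaving the text alone: under either reading the printed sentences are false.

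**Conclusion.** The concern holds. On the stated inputs, 36 participants give 0.90 power rather than 0.80, and a 10% allowance cannot reduce 36 to 28. The first point rests on the inferred paired t-test, but no alternative tried that keeps the stated two-sided 0.05 rescues it. The second needs no assumption about the test.

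The trial is not seriously underpowered for the before-after change. The planned 30 is above 28 and does not contradict it. With 27 evaluable, the difference detectable at 0.80 power is 1.01 instead of 1.00. The fault lies in the stated justification, which has to be corrected because it is the only one the plan gives.

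None of these figures is power for retinol against placebo. The design is within-person ("Participants will apply treatment to one arm and placebo to the other arm"), and the documents give no SD for the between-arm contrast. As an illustration only, assume that the change in each arm has SD 1.8, that the contrast is also 1.00, and that the arms correlate r within a person. The SD of the contrast is then 1.8√(2(1−r)), and power with 27 evaluable is 0.50 at r = 0, 0.62 at r = 0.25, 0.79 at r = 0.5 and 0.98 at r = 0.75.

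**What to change.** The investigator should first check the original calculation: the intended digit in 36, the method used, and whether 28 was meant as evaluable or enrolled. Then replace the two sentences with wording such as:

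> With 28 evaluable participants, a paired t-test at two-sided alpha 0.05 has 0.81 power for a mean change of 1.00 unit in fine wrinkling score from before to after treatment, if the SD of the changes is 1.8. We will enrol 30; with 10% dropout, 27 evaluable participants give 0.79 power.

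Remove 36 unless a different SD, difference or power that supports it is stated. These replacement figures are correct on the stated inputs however the 28 arose. Do not describe them as power for the retinol-versus-placebo comparison.

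The cost is one check and two sentences, with no extra enrolment. The downside is that the plan then shows 0.79 instead of 0.80 after dropout.

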Furthermore, studies on retinol to date in humans have occurred largely in white population even though individuals of Asian descent represent the majority of the world population. The potential effects of retinol on individuals of Asian descent are uncharacterized and represent an untapped potential to explore differences in aging across ethnic groups.

While prior studies have indicated an increase in glycosaminoglycans (GAGs) and collagen after topical retinol usage (Kafi *et al.*, 2007), the true breadth of anti-aging effects including the mechanisms by which these effects are controlled has not been explored. It is possible that topical retinol has additional effects on major pathways of skin aging, such as NFkB related genes (Chang *et al.*, 2013) as well as previously unknown aging pathways. This study aims to discover the molecular basis of rejuvenation effects of retinol so that new topical agents can be identified that might mimic aspects of the retinol rejuvenation effect. We aim to do this in a Han Chinese cohort, as this is the most populous ethnic group among the East Asian population. Given the similarity in haplotype of Han Chinese with Korean and Japanese populations, these latter groups will be included as well.

Objective:

To discover new pathways of rejuvenation using topical vitamin A application on naturally aged in East Asian women.

Specific Aims:

Specific Aim 1: To discover molecular pathways of skin rejuvenation by identification of gene expression profiles after topical vitamin A in East Asian women

Specific Aim 2: To identify changes in wrinkling and biometrics associated with skin rejuvenation after topical vitamin A application in East Asian women

Specific Aim 3: To identify type and severity of adverse events associated with topical retinol usage

Materials and Methods

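### The fine wrinkling and other photographic scores have only a before/after comparison within each arm; the randomized retinol-versus-vehicle contrast is neither stated nor powered for them

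*Combined protocol and SAP*

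**What the plan says.** - **Design.** Under Enrollment Visit (VISIT 2): "Participants will apply treatment to one arm and placebo to the other arm based on computer generated randomized assignment". Thirty older participants are to be treated.
- **Aim.** "Specific Aim 2: To identify changes in wrinkling and biometrics associated with skin rejuvenation after topical vitamin A application in East Asian women".
- **Power.** Statistical Considerations sizes the trial on fine wrinkling (0 to 9 scale) for "detecting a difference of 1.00 unit on mean value before and after treatment", two-sided 0.05, power 0.80, "assuming a standard deviation of differences to be 1.8". Vehicle is not mentioned.
- **Photographic scores** (fine wrinkling, dyspigmentation, surface texture). Anticipated Results forecasts "statistically significant differences in mean score of these parameters between pre- and post- treatment groups for both vitamin A and placebo". No other comparison is given for them anywhere.
- **Other outcomes.** Histology: "treatments groups for topical vitamin A versus placebo will be compared". Cutometry and TEWL: means and SDs "before and after topical vitamin A treatment will be calculated and compared to placebo", followed by "We anticipate there will be statistically significant differences in the mean scores in cutometry and TEWL measurements between treated and placebo groups". The gene expression paragraph also names placebo as the comparator.
- **Rank.** Fine wrinkling is primary among the clinical endpoints in Statistical Considerations and tertiary in Anticipated Results.

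**The concern.** Randomizing left and right arms within a person makes one comparison free of anything that affects both arms alike: retinol minus vehicle. For the endpoint that sizes the trial, the plan does not state that comparison. It describes change over time on each lotion.

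Change over time on retinol mixes the retinol effect with whatever else moved between baseline and Week 12. The documents suggest two possible sources of shared change. The vehicle is itself a body moisturizer, begun after a period in which arm moisturizers were barred for 2 weeks. Entry for the older group also needs a wrinkling score of 7 or more, so regression to the mean is possible if the qualifying score is also the analysis baseline. Neither is shown to operate, but the plan does not need convincing: it forecasts a significant change on placebo.

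If the stated comparison is followed, a significant before/after result on retinol is what the plan would expect from vehicle too, so the wrinkling part of Aim 2 goes unanswered. If it is not followed, the contrast is left to be chosen after the data are seen. In either case the 0.80 power does not describe the randomized comparison.

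**Working it through.** **1. The plan's own figure.** Inputs from Statistical Considerations: difference 1.00, SD of differences 1.8, two-sided 0.05, power 0.80.

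- Normal approximation: n = ((1.960 + 0.842) × 1.8 / 1.00)² = 25.4, so 26.
- Exact paired t-test (noncentral t): n = 28, power 0.81.
- At the stated 36, paired-t power is 0.90, not 0.80.

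The 36 does not reproduce, and a fall from 36 to 28 after allowing for dropout cannot be right. That is a separate defect, and neither number is used below. I take n = 30 × 0.9 = 27 completers, with n = 30 in brackets.

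**2. What a shared change does to the before/after test.** The plan gives no size for the vehicle change. Assume that 1.8 also holds for the vehicle arm. A significant change on vehicle then needs an observed mean change of at least

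t(0.975, n−1) × 1.8 / √n = 2.056 × 1.8 / √27 = 0.71 [2.045 × 1.8 / √30 = 0.67].

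That is about 70% of the 1.00 unit for which the trial is powered. Now assume no retinol effect and a true change shared by both arms. The noncentral t gives the probability that the retinol before/after test is significant:

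| Assumed shared change | n = 27 | n = 30 |
|---|---|---|
| 0.25 | 0.11 | 0.11 |
| 0.50 | 0.28 | 0.31 |
| 0.75 | 0.55 | 0.60 |

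The paired retinol-minus-vehicle test stays at 0.05, because the shared change cancels. A simulation with shared changes of 0.5, 0.71 and 1.0, and between-arm correlations of 0, 0.5 and 0.75, gave rejection rates of 0.049 to 0.051 throughout.

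**3. Power for the randomized contrast.** No SD is given for retinol minus vehicle. Assume that each arm's change has SD 1.8 and that the two changes have correlation ρ within a person. Then

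SD of the difference in change = 1.8 × √(2(1 − ρ)).

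| ρ (assumed) | SD | Power, net 1.00 | Difference detectable at 0.80 |
|---|---|---|---|
| 0 | 2.546 | 0.50 [0.55] | 1.43 [1.35] |
| 0.25 | 2.205 | 0.62 [0.67] | 1.23 [1.17] |
| 0.5 | 1.800 | 0.79 [0.84] | 1.01 [0.95] |
| 0.75 | 1.273 | 0.98 [0.99] | 0.71 [0.67] |

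Power of 0.80 for a net 1.00 unit needs ρ of about 0.51 [0.45].

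The 1.00 does not carry over automatically either, since it is a before/after difference. If vehicle also improves and the net difference is 0.50, power with 27 completers is 0.17, 0.29 or 0.50 at ρ = 0, 0.5 or 0.75.

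**The case against.** The photographic sentence is a forecast under Anticipated Results and not an analysis rule. Everything around it points to a vehicle-controlled intent: randomized sides, blinded participants, blinded reading of photographs, and placebo named as comparator for histology, cutometry, TEWL and gene expression. The histology sentence uses similar before/after phrasing and still compares with placebo, so this one may just be loosely written. The objective and Aim 1 are molecular, and one paragraph calls fine wrinkling tertiary. The power figures rest on a correlation that the documents do not give, and so show no shortfall.

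Much of this is fair. What is shown is that the right contrast is missing, not that the investigator deliberately chose a wrong one. The power tables are a range, not a finding that the trial is too small. The shared-change probabilities depend on assumed shifts; a true shift placed at the 0.71 threshold would give about one half by construction, so that value says nothing about this trial.

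What remains is enough. This document is both protocol and SAP, and it contains no other comparison for these scores. Its wording, covering vitamin A and placebo each before and after, reads as within-arm. Fine wrinkling is the only endpoint used to size the study, so it is not peripheral.

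**Conclusion.** The concern holds and needs correction before analysis. For fine wrinkling, dyspigmentation and surface texture, the only stated comparison leaves out the randomized control and, followed as written, could not attribute a change to retinol. This rests on the text alone and on the plan's own expectation of change on placebo.

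The size depends on assumptions. With SD 1.8 in each arm and 27 completers, a shared change of 0.25 to 0.75 units would produce a significant retinol before/after result with probability 0.11 to 0.55 when retinol does nothing. Power for retinol minus vehicle at a net 1.00 unit lies between 0.50 and 0.98 for correlations from 0 to 0.75. It may be lower or higher than 0.80; the documents cannot settle which. The primary/tertiary wording alone is a point of clarification: both labels could hold if the endpoint ranks first among clinical endpoints and third overall, but no ranking is stated.

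**What to change.** 1. Name the analysis for the three photographic scores: the within-participant retinol-minus-vehicle difference in change from baseline to Week 12, by paired t-test. If baseline scores will not exist for each treated arm, name the Week 12 retinol-minus-vehicle difference, which the left/right randomization supports. A covariate-adjusted mixed model is optional.
2. Make before/after change within each arm descriptive.
3. Restate power, or the detectable difference, for the chosen contrast at the planned 30 participants, with a justified between-arm SD or a range. Do not relabel 1.00 and 1.8 as between-arm values. If the Week 12 difference is chosen, it needs its own SD; the table above applies to change scores only.
4. Give fine wrinkling one stated rank.

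The cost is text edits and a new power line, with no added participants and no change to randomization or blinding. The drawback is that the power statement may look worse: with 27 completers and a between-arm correlation below about 0.51, 0.80 power for a net 1.00 unit is not reached, and the larger detectable difference should be stated instead.
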